1.2.2 Informative Component

The parameters of the informative component are listed below:

$$\mu = (-1.4199504, -0.7110435)$$
$$\Sigma = \begin{pmatrix} 0.173397 & 0.0023933 \\ 0.0023933 & 7.3526064 \times 10^{-4} \end{pmatrix}$$

The minimally informative component makes the design robust against surprising deviations from the informative component.

[figure not shown]
A minimally informative prior component will be constructed based on the assumed not toxic and toxic doses. It is conservatively assumed that would be very unlikely (with a 60% confidence) that 10% or higher DLT rates are associated with the first dose of monotherapy dose-escalation and that it would be very unlikely (with 90% confidence) that a 25% or lower DLT rates are associated with the dose of 400 mg.

The parameters of the minimal informative prior are listed below:

$$\mu = (-0.0983878, -0.4150429)$$
$$\Sigma = \begin{pmatrix} 1.7525039 & -0.0052047 \\ -0.0052047 & 0.0185343 \end{pmatrix}$$

The plot of the prior distribution used for the study can be seen in [Figure 1](#) and it will be the primary prior distribution used to determine the dose-escalation decisions.

Figure 1: Prior Plot

In black the informative, in blue the minimal informative and in red the mixture prior dose-toxicity relationship.

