4.1.2.2 Part II: Multiple-Ascending Dose-Escalation (Multiple Participant Cohorts)

A modified continual reassessment method with overdose control (mCRM-EWOC) will guide the dose-escalation to determine the MTD, by using primary safety variables (e.g., DLT). This model-based design assigns participants to dose-levels and defines the MTD based on the estimation of the target toxicity level by a model depicting the dose-toxicity relationship. The dose-toxicity relationship is described by a two-parameter logistic regression model, which is continuously updated as additional participant information becomes available.

The prior distribution for the parameters of the DLT dose-response curve will be a mixture of informative and minimally informative components. The minimally informative component makes the design robust against unforeseen deviations from the informative component and will be constructed based on the assumed not toxic and toxic doses. For the dose toxicity relationship of the minimally informative component, it is conservatively assumed that it would be very unlikely that 10% or higher DLT rates are associated with the first dose of the monotherapy dose-escalation and that it would be very unlikely that a 25% or lower DLT rate is associated with a dose of 400 mg (additional details provided in [Appendix 8](#)). The informative component will be the posterior distribution of the CEA TCB (*cibisatamab*) monotherapy toxicity data without obinutuzumab pre-treatment, as of cutoff date 20 July 2017, approximated with a bivariate normal distribution. The two components will be mixed in a 10/90% ratio (informative prior component 10%; minimally informative component 90%). Further details are provided in [Appendix 8](#).

The MTD is defined as the dose with the highest probability that the DLT rate is within the target of 20% to 35%, and a relatively low probability (< 25%) that the DLT rate is above 35%.

- Dose-escalation to IV MTD

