Such model-based designs have been successfully applied in many Phase I dose-escalation studies ([Schöffski et al 2004](#); [Le Tourneau et al 2009](#); [Neuenschwander et al 2008](#)).

In addition, hypothetical dose-escalation runs using the design and simulations demonstrate the validity of the operating parameters of the design as implemented for this study ([Appendix 8](#)).

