1.2.1 Model Prior

For the multiple participant cohort dose-escalation, the prior distribution will be a mixture of prior informative and minimally informative components. The informative component will be the posterior distribution of the CEA TCB (*cibisatamab*) monotherapy toxicity data (without obitinuzumab pre-treatment), as of cutoff date 20 July 2017, approximated with a bivariate normal distribution. A minimally informative prior «neutral» component will be constructed based on the assumed not toxic and toxic doses. The two components will be mixed in a 10/90% ratio ($p_{i_1} = 0.25$) (informative prior component 10%; minimally informative component 90%).

$$(\alpha, \log(\beta))^T \sim \pi_1 N_1(\mu_1, \sigma_1) + (1-\pi_1) N_2(\mu_2, \sigma_2)$$

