1.4.1 Dose-toxicity Scenarios

In these simulations (Figure 2), the starting dose of 0.5 mg is assumed. Scenario 1 reflects the current expected toxicity of this compound. The others are intermediate or extreme scenarios. The MTD (upper 35% DLT toxicity interval) ranges from 69 mg (low MTD) to 438 mg (illustrating a scenario for which toxicities are expected only at the highest dose).

Figure 2 Dose Toxicity Scenarios

[figure not shown]

Table 2: Scenarios Parameters

Scenario	Target Dose Interval, mg	Parameters
1	48-75	alpha = -0.11, beta = 1.74
2	136-199	alpha = -2, beta = 2
3	247-299	alpha = -5, beta = 4
4	82-121	alpha = -1, beta = 2
5	375-438	alpha = -8, beta = 5
6	23-69	alpha = -0.36, beta = 0.7

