1.4.2 Simulation Results

For each of the scenarios, 500 trials were simulated.

The design is evaluated using the following criteria: the MTD chosen, the number of participants treated at doses higher than the MTD, and the total number of participants treated. The result of the simulations is summarized in [Table 3](#).

[figure not shown]
Table 3: Simulation Study Results Summary

Scenario	Target Dose Interval in True Scenario, mg	Overall N of Participants*	N Participants Treated above Target Toxicity Interval*	Proportions of DLTs in the Trials, %*	Doses Selected as MTD, mg*	Dose most often Selected as MTD, mg
1	48-75	29 (24, 36)	7 (0, 12)	16.4 (12.5, 21.2)	72.3 (44.5, 100)	50
2	136-199	34 (30, 39)	6 (0, 12)	13 (10, 16.7)	186.7 (120, 250)	150
3	247-299	34 (30, 39)	6 (3, 9)	10.5 (6.7, 13.9)	290.3 (250, 350)	250
4	82-121	31 (27, 36)	4 (0, 9)	14.8 (11.1, 18.2)	111.7 (75, 150)	150
5	375-NA	37 (33, 45)	0 (0, 0)	7.3 (5.6, 9.5)	384 (350, 400)	400
6	23-69	28 (21, 36)	2 (0, 9)	18.1 (14.3, 22.2)	45.1 (14, 85)	25

[figure not shown]
* mean and 10 and 90 % quantiles.

In addition, illustrated here separately for each true dose toxicity scenarios the true toxicity curve from the scenario with the average model fit from the 500 simulation runs.

[figure not shown]
Scenario 1: True MTD 74.64 Parameters $\alpha=-0.11$, $\beta=1.74$

[figure not shown]
Scenario 2: True MTD 199.47 Parameters $\alpha=-2$, $\beta=2$

[figure not shown]
Scenario 3: True MTD 298.99 Parameters alpha=-5, beta=4

[figure not shown]
Scenario 4: True MTD 120.98 Parameters alpha=-1, beta=2

Scenario 5: True MTD 437.62 Parameters $\alpha=-8$, $\beta=5$

Scenario 6: True MTD 69.07 Parameters $\alpha=-0.36$, $\beta=0.7$

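### The 90% prior component is wide on the position of the dose-toxicity curve but tight on its slope, and Table 3 does not report how often the selected MTD is over-toxic

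*Combined protocol and SAP*

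**What the plan says.** Part II escalation is guided by a two-parameter logistic model with a mixture prior. Section 4.1.2.2 of the protocol says: "The minimally informative component makes the design robust against unforeseen deviations from the informative component". Appendix 8, Section 1.2.2, repeats this almost word for word: "The minimally informative component makes the design robust against surprising deviations from the informative component". Neither sentence is limited to one parameter. Section 1.2.2 prints the component's covariance matrix; its lower row ends "0.0052047 & 0.0185343", so the variance of log slope is 0.0185. On weights, Appendix 8, Section 1.2.1, says "The two components will be mixed in a 10/90% ratio", and the same line prints a weight parameter of 0.25.

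Section 1.4.1 lists six true curves and states: "Scenario 1 reflects the current expected toxicity of this compound". Its slope is 1.74. Section 1.4.2 judges the design on "the MTD chosen, the number of participants treated at doses higher than the MTD, and the total number of participants treated". Table 3 gives means, 10% and 90% quantiles and the most often selected MTD. It does not give the share of trials whose selected MTD is below, inside or above the 20-35% target. Section 4.2.1 concludes that the "simulations demonstrate the validity of the operating parameters of the design as implemented for this study".

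**The concern.** A component described as minimally informative and as the source of robustness should let the data correct the model where the prior is wrong. If its slope is almost fixed, roughly 30 participants cannot move it, and the limit on overdose probability (below 25%) then depends on that assumed slope. Determining the MTD and/or OBD is a primary objective, and Appendix 8 is the evidence offered that the model can do it. The people taking escalation decisions should know where the model adapts and where it does not. They should also know how often, on the sponsor's own curves, it ends at a dose above target.

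**Working it through.** **Inputs.** Appendix 8, Section 1.2.2: minimally informative component, mean of log slope -0.4150429, variance 0.0185343, variance of alpha 1.7525039; informative component, mean of log slope -0.7110435, variance 0.00073526, variance of alpha 0.173397. Section 1.2: reference dose 100 mg. Section 1.4.1: scenario parameters. Section 1.4.2: Table 3.

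**1. Reproducing the plan's target intervals.** The dose at DLT rate p is 100 × exp((logit p − alpha)/beta). At p = 0.20 and 0.35 this gives 48-75, 136-199, 247-299, 82-121, 375-438 and 23-69 mg, matching Table 2.

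**2. Prior slope ranges, exp(mean ± 1.96 × SD).**
- Minimally informative: SD = √0.0185343 = 0.136, range exp(−0.415 ± 0.267) = 0.51 to 0.86.
- Informative: SD = √0.00073526 = 0.0271, range exp(−0.711 ± 0.053) = 0.47 to 0.52.
- Distance from the minimally informative mean, (ln beta + 0.415)/0.136: slope 1.74 is 7.1 SDs away, 2 is 8.1, 4 is 13.2, 5 is 14.9 and 0.7 is 0.4. Only Scenario 6 lies inside.

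These ranges do not depend on the mixture weight.

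**3. Prior on position.** SD of alpha is √1.7525 = 1.32 against √0.1734 = 0.42, so on this axis the component does add robustness.

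**4. Can data move the slope?** Illustrative data (an assumption): 0/3 DLTs at each of 1.6, 3.2, 6.4, 12, 20 and 40 mg, then 6/12 at 80 mg. Numerical integration with the printed mixture at weight 0.10 gives posterior mean slope 0.68 (95% interval 0.49-0.90) and a mean DLT rate at 80 mg of 33%, against 50% observed. If the SD of log slope in the 90% component is set to 1 (same mean, zero covariance), the slope is 2.47 (0.49-6.72).

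**5. True DLT rates at Table 3's own doses, p = 1/(1 + exp(−(alpha + beta × ln(dose/100)))).**

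| Scenario | Mean selected MTD | True rate | 90% quantile | True rate |
|---|---|---|---|---|
| 1 | 72.3 mg | 34% | 100 mg | 47% |
| 2 | 186.7 mg | 32% | 250 mg | 46% |
| 3 | 290.3 mg | 32% | 350 mg | 50% |
| 4 | 111.7 mg | 31% | 150 mg | 45% |
| 5 | 384 mg | 22% | 400 mg | 26% |
| 6 | 45.1 mg | 29% | 85 mg | 38% |

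All six means are inside target. By definition of the 90% quantile, at least 10% of trials select that dose or a higher one. For "Scenario 4: True MTD 120.98 Parameters alpha=-1, beta=2", the most often selected MTD in Table 3 is 150 mg, with a true rate of 45%.

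**6. Which inputs produced the tables?** Section 1.4.1 says the simulations start at 0.5 mg. Section 4.1.2.2 starts Part II at 1.6 mg if that dose was reached and considered safe in Part I, and the mock runs in Table 1 begin at 1.6 mg. An independent re-implementation (1000 trials per scenario) gave these mean N for Scenarios 1-4:
- Table 3: 29, 34, 34, 31.
- Start 1.6 mg: 28.7, 32.9, 33.5, 30.4.
- Start 0.5 mg: 33.5, 37.3, 39.6, 34.6.

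On weight, 0.10 reproduces 24 of the 36 Table 1 cells exactly and 0.25 reproduces 20. From a 1.6 mg start, mean selected MTD in Scenarios 1 and 4 is 73.5 and 114.0 mg at 0.10, and 81.7 and 123.2 mg at 0.25 (Table 3: 72.3 and 111.7). The tables therefore look like weight 0.10 and a 1.6 mg start, but only the sponsor can confirm this.

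**The case against.** The robustness claim is relative to the informative component, and the second component is wider on both axes: SD of log slope 0.136 against 0.027, about five-fold. That is true, and on position the claim stands. On slope, a range five times wider that still misses the expected curve by 7 SDs gives no practical protection.

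The sponsor did simulate steep curves, printed every parameter, and the mean selected MTD is in target throughout. That also stands. The gap is in what is reported about the spread of selections.

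The Scenario 4 mode owes something to the dose grid, which runs 100, 120, 150, 200 mg. In-target selections split over several doses while higher ones collect at 150 mg. It is not evidence of a slope effect alone. Scenario 6, whose slope is inside the prior range, also has a 90% quantile slightly above target.

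A reader might infer that the design picks an over-toxic dose in a third to a half of trials. The documents do not support that. Grid doses 75, 200 and 300 mg have true rates of 35.2%, 35.1% and 35.3% in Scenarios 1, 2 and 3 and count as overdoses at a strict 35% cut. In one set of runs, moving the cut to 36% lowered the share from 40% to 28% in Scenario 2 and from 44% to 21% in Scenario 3. Shares above 40% ranged from about 10% to 51% per scenario across implementations, so they are indicative only.

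A reader might also infer that the fixed slope always makes the model optimistic. It does not: with an extreme 0/30 at 50 mg and 30/30 at 100 mg, the model puts a 91% probability on 50 mg exceeding 35%, which is excess caution. Nor does comparing a posterior overdose probability with a frequency under one fixed curve test calibration. Finally, Section 4.2.1 lets clinical judgment override the model.

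**Conclusion.** The point holds as a matter of description and reporting. The robustness statements are right for curve position and wrong for slope: neither component's 95% range contains the slope of Scenarios 1-5. This follows from printed parameters and needs no simulation. The validity statement rests on a table that omits the frequency of over-toxic selection, while that table's own quantiles imply at least 10% of trials at a true DLT rate of 45-50% in each of Scenarios 1-4. That figure assumes only that Tables 2 and 3 are correct as printed.

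A reader might go further and conclude that the narrow slope prior must be replaced. The evidence does not show that. In re-runs with the SD of log slope set to 1, above-40% selections fell, but selection below 20% DLT in Scenario 2 rose from 8-14% to 40-44%. In an assumed low-MTD case (35% DLT at 3 mg, slope 0.7), in-target selection fell from 54% to 32%. The narrow slope is a defensible trade-off, provided it is described as one.

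The two values for the mixture weight, and the two for the starting dose, are separate inconsistencies in the same evidence. They do not affect the slope ranges.

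**What to change.** 1. In Section 4.1.2.2 and Appendix 8, Section 1.2.2, limit the robustness statement to the position of the curve. Add that the component's 95% prior slope range is 0.51-0.86 and does not contain the slopes of Scenarios 1-5. In Section 4.2.1, say that the simulations describe the operating parameters rather than prove them valid.
2. Add to Table 3 the percentage of trials selecting an MTD with a true DLT rate below 20%, in 20-35%, above 35% and above 40%. The last column should be required, because grid doses at 35.1-35.3% make the above-35% column hard to read alone.
3. Reconcile the mixture weight (10/90% against 0.25) and the simulated starting dose (0.5 mg against 1.6 mg). State which values produced Tables 1 and 3.

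Cost: a few sentences, and four columns tabulated from the existing 500 trials per scenario. Tables 1 and 3 need rerunning or relabelling only if the values used differ from the plan. No change to the prior or the escalation rules is requested.

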1.2.3 Dose Grid

The following dose grid has been used: from 0.5, to 10 by 0.1, from 11 to 20 by 1, 25, 27, from 30 to 100 by 5, 120, 150 to 400 by 50.

1.2.4 Maximum Dose-Increments

The following rules for selecting the maximum allowed dose-increment will be applied.

Relative to DLT:

Until 1 DLT an increment of 100%, from 1 DLT an increment of 50% maximum are allowed.

The lower increment between the ones described above will then be chosen as maximum allowed dose-increment.

1.2.5 Stopping Rules

The trial will be halted if either at least 6 participants have been observed at a dose close to MTD (i.e., a dose differs by 20%) and the posterior probability that

$[0.2 \leq \text{Prob}(\text{DLT} \mid \text{dose}) \leq 0.35]$ for the next best dose is above 40% or the maximum of 60 DLT-evaluable participants is reached.

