The starting-dose for the initiation of Part II IV dose-escalation will be determined by Part I and RO7172508 will be initially given Q3W. Dose-escalation will continue based on safety until determination of the MTD or the planned maximum dose of 400 mg. If on-target toxicity is reported predominantly in the first cycle of treatment, fractionated dosing may be implemented for the first cycle to improve tolerability.

Once the IV schedule has shown RO7172508 preliminary clinical activity, defined by partial response (PR) or better, according to RECIST v. 1.1 (Appendix 6), or the MTD has been established and is equal to or above 2 mg, the SC multiple-ascending dose-finding cohorts could be initiated. The starting-dose and regimen (QW or Q3W) for SC administration will be proposed based on the evaluation of the safety and PK data observed following IV administration but will not exceed the highest safe dose tested in the IV Q3W dose escalation; however, due to practical considerations, a minimum dose of 2 mg is defined for a single SC administration. In addition, the QW SC starting-dose will not exceed one third of the IV MTD or of the highest safe IV dose tested.

In Part II, a modified continual reassessment method with overdose control (mCRM-EWOC) will guide the dose-escalation part to determine the MTD, by using primary safety variables (e.g., DLT).

The MTD is defined as the dose with the highest probability that the DLT rate is within the target of 20% to 35%, and a low probability ($< 25\%$) that the DLT rate is above 35%.

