4.1.4 Stopping Rules Criteria

The dose-escalation will be halted if, for each route of administration or schedule, either:

- The MTD has been reached as determined by the model ([Appendix 8](#)) and at least 6 participants have been already dosed at the current estimate of the MTD ($\pm 20\%$).
- The maximum of 60 DLT-evaluable participants is reached.

Due to the exploratory nature of this clinical study, any part of its conduct can be discontinued at any time at the discretion of the Sponsor. This will not constitute a

premature termination of the study. The Sponsor will notify the Investigators and Health Authorities if the study is discontinued or the development program is terminated.

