9.2 SAMPLE SIZE DETERMINATION

Part I will enroll up to approximately 5 participants. The sample size is determined by the dose-increment steps implemented in this part.

In Part II, it is anticipated that a maximum of approximately 60 participants will be enrolled in each dose-escalation phase (IV and SC) (up to approximately 75 participants if one or several cohorts are expanded). *In case the OBD dose cohort is expanded both with and without obinutuzumab, an additional 15 participants may be enrolled.*

The probability of observing at least one event out of 15 participants for a true underline rate of 10% is 79% while out of 5 patients is 41%. Probabilities of the occurrence of 1 or more events for different ranges of true underline rates and different participant numbers are summarized in [Table 20](#).

The exact sample size for the dose-escalation part cannot be pre-determined and depends on the number of cohorts needed to reach the MTD (or highest safe dose if MTD is not reached).

Table 20 Probabilities for Observing Adverse Events

Total N of Participants	True AE Probability	Probability that AE ≥ 1	Probability that AE ≥ 2	Probability that AE ≥ 3
15	0.1	0.79	0.45	0.18
	0.2	0.96	0.83	0.60
	0.3	1.00	0.96	0.87
	0.4	1.00	0.99	0.97
	0.5	1.00	1.00	1.00
10	0.1	0.65	0.26	0.07
	0.2	0.89	0.62	0.32
	0.3	0.97	0.85	0.62
	0.4	0.99	0.95	0.83
	0.5	1.00	0.99	0.95
5	0.1	0.41	0.08	0.01
	0.2	0.67	0.26	0.06
	0.3	0.83	0.47	0.16
	0.4	0.92	0.66	0.32
	0.5	0.97	0.81	0.50

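### Appendix 8 has no exit short of 60 participants when 400 mg is tolerated with almost no DLTs, which conflicts with how the synopsis ends escalation

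*Combined protocol and SAP*

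**What the plan says.** - **Appendix 8, Section 1.2.5** gives two exits. The first needs both at least 6 participants within 20% of the MTD and a posterior probability of the 20–35% DLT interval that "for the next best dose is above 40% or the maximum of 60 DLT-evaluable participants is reached"; the second half of that quote is the other exit. Nothing is said about a tolerated highest dose.
- **Synopsis**: "Dose-escalation will continue based on safety until determination of the MTD or the planned maximum dose of 400 mg".
- **Sections 4.1 and 9.2** foresee that no MTD may be found. Section 9.2 adds "or highest safe dose if MTD is not reached".
- **Section 4.1.4** requires that the model of Appendix 8 has reached the MTD and that "at least 6 participants have been already dosed at the current estimate of the MTD", within 20%, or that 60 DLT-evaluable participants have been treated. It prints no 40% figure and no stop at 400 mg.
- **Sections 4.1.2.2 and 4.1.3** carry the stopping rules over to the SC escalation and to any escalation with obinutuzumab pre-treatment.
- **Appendix 8, Section 1.2.3** makes 400 mg the top of the dose grid.

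**The concern.** The 40% condition asks for evidence that the next dose is toxic enough to lie in the target interval. At lower doses a clean cohort leads to escalation. At 400 mg it cannot, and each further clean cohort lowers the probability that has to rise. Followed literally, the rule keeps enrolling at the highest dose in a first-in-human trial for a question that is already settled.

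At stake are the number treated at the top dose, agreement between the protocol body and its statistical appendix, and whether the simulations cover an outcome the protocol itself foresees.

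**Working it through.** **Inputs.** From Appendix 8: logit p(d) = α + β ln(d/100); the two printed bivariate normal components for (α, log β); the mixture ("The two components will be mixed in a 10/90% ratio", although the same sentence also prints 0.25, so both weights were run); the dose grid; increments of at most 100%, or 50% from the first DLT; cohorts of 3. From Section 4.1.2.2: the next dose has the highest probability of a 20–35% DLT rate, subject to P(rate > 35%) < 0.25. The posterior is prior × Π p(d)^y (1 − p(d))^(n−y), integrated numerically.

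**Reproducing the plan first.** At the 10/90 weight, the mock-run rows with 0 or 1 DLT match within one grid step (for 2–3 DLTs the largest gap is 12 versus 15 mg). Mean N in Table 3, from 500 simulated trials started at 1.6 mg:

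| Scenario | 1 | 2 | 3 | 4 | 5 | 6 |
|---|---|---|---|---|---|---|
| Table 3 | 29 | 34 | 34 | 31 | 37 | 28 |
| Recomputed | 29.4 | 33.8 | 34.7 | 31.4 | 38.2 | 28.6 |

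The 10% and 90% quantiles for Scenario 5 are (33, 57) recomputed and (33, 45) printed, so that upper tail agrees less well. The 0.5 mg start stated in Appendix 8, Section 1.4.1 does not reproduce the table (Scenario 5 gives 42.2, Scenario 1 gives 33.6), so 1.6 mg is used below. With the 40% condition dropped, Scenario 5 falls to 33.3 (33, 33). The condition therefore already binds at 400 mg in the plan's own setting.

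**Is a tolerated 400 mg simulated?** Scenario 5 has the highest MTD. Its rate at 400 mg is 1/(1 + exp(8 − 5 ln 4)) = 25.6%, inside the target. No scenario puts 400 mg below 20%.

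**Clean escalation.** Nine levels below 400 mg (1.6, 3.2, 6.4, 12, 20, 40, 80, 150, 300) with 3 participants each make 27. Probability that 400 mg lies in the target interval, with no DLT below it:

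| DLTs/n at 400 mg | 10/90 weight | 0.25 weight |
|---|---|---|
| 0/3 | 0.256 | 0.317 |
| 0/6 | 0.173 | 0.223 |
| 0/9 | 0.111 | 0.148 |
| 0/33 | 0.001 | 0.002 |
| 1/6 | 0.356 | 0.420 |
| 1/9 | 0.265 | 0.324 |
| 2/6 | 0.513 | 0.568 |
| 2/9 | 0.443 | 0.503 |
| 2/12 | 0.353 | 0.414 |

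With no DLTs the value falls steadily and never reaches 0.40 under either weight. With one DLT at 400 mg it is not met at 10/90; at 0.25 it is met at 1/6 only. So a clean escalation runs to 60, with 60 − 27 = 33 at 400 mg. Ending after 6 there gives 27 + 6 = 33 in total. The difference is 60 − 33 = 27.

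**When chance DLTs end it.** Two DLTs in the first 6 or 9 at 400 mg meet the condition. At a true 5% rate the chance of at least two is 1 − 0.95⁶ − 6(0.05)(0.95⁵) = 3.3% in 6, and 7.1% in 9; at 10% it is 11.4% and 22.5%. DLTs at lower doses can also do it: one each at 150 and 300 mg, then 0/3 at 400 mg, stops at N = 36 with probability 0.475.

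**Share of trials reaching 60.** The true rates at 400 mg are assumptions, since the documents give none below target.

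| Rate at 400 mg | Logistic, slope 5 (500 trials) | Step: p from 300 mg up, p/2 below (300 trials) |
|---|---|---|
| 0% | 100% | – |
| 2% | 98% | – |
| 5% | 90% | 74% |
| 10% | 65% | 35% |
| 15% | 40% | – |
| 20% | 18% | – |

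A second set of 500 at 10%, slope 5, gave 69%, which is within simulation error; slope 1 gave 53%. In the step setting, mean N is 55 at 5% (38 with a stop after 6 at 400 mg) and 48 at 10% (41). The mean selected dose is the same with and without that stop: 397 mg at 5%, 364 mg at 10%.

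**The case against.** Three points on the other side stand and limit the finding.

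- **The condition can be met.** A reader might infer that it can never be satisfied at a well-tolerated 400 mg. That is exact only for no DLTs, or one at 400 mg under the 10/90 weight. At a 10% rate, which many would still call tolerable, between about a third and two thirds of trials stop before 60.
- **Section 4.1.4 is not plainly contradicted.** A reader might see a third, separate rule there. It omits the 40% figure, and read alone would stop a clean escalation at 33, but it refers to Appendix 8 for whether the MTD has been reached, has the same cap, and has no 400 mg stop either. The conflict there is partial.
- **Running to 60 is implied, not compelled.** Section 4.2.1 lets clinical judgment override the model, each cohort needs a joint sponsor and investigator decision, and Section 4.1.4 lets the sponsor discontinue any part at any time.

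The case is also remote on the plan's own expectations: Section 4.3.1 equates about 25 mg with the exposure at the related agent's MTD, and Scenario 1, the expected one, targets 48–75 mg. Yet Section 4.3.1 extends the range to 400 mg because clinical potency may differ from in vitro potency, and Section 9.2 allows for no MTD being found. Discretion permits an earlier end but gives no criterion for one.

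Finally, the selected dose did not change in the simulations, and enrolment stays within the declared 60.

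**Conclusion.** The gap is real but bounded. With DLTs absent or very rare at 400 mg, Appendix 8, Section 1.2.5 has no exit before 60. The largest effect is 27 additional participants at 400 mg (33 rather than 6), who cannot raise the dose. The share of trials reaching the cap is about 74–90% at a 5% DLT rate and 35–65% at 10%, depending on the assumed curve.

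The clear conflict is with the synopsis and with the provision in Sections 4.1 and 9.2 for a highest safe dose when no MTD is found. The documents do not support saying that the condition is unattainable, that Section 4.1.4 directly opposes the appendix, or that 33 participants must be treated at 400 mg.

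The figures rest on the printed prior at the 10/90 weight, a 1.6 mg start, cohorts of 3 and the rule applied without override. They concern IV dosing only: no SC prior is printed, so no SC figure can be derived. This should be fixed; it does not bias the dose selected.

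**What to change.** Reconcile the synopsis, Section 4.1, Section 4.1.4 and Appendix 8, Section 1.2.5 so that all four state one rule for how escalation ends when the highest permitted dose is tolerated and the 40% condition is not met. The 6-participant minimum already in the protocol is an available basis; the choice is the sponsor's. State that the same rule governs the escalations that inherit it (SC, and with obinutuzumab pre-treatment), each with its own maximum dose.

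Add to Table 3 at least one scenario with the DLT rate at 400 mg below 20%, reporting total N and the number treated at 400 mg. State the prior weight and starting dose actually used.

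The cost is a sentence in each place and one more simulation. If the agreed rule ends escalation before the cap, enrolment falls.
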